2.3.2. Benefit Assessment

The healthy participants will receive no clinical benefit for participation in this study.

2.3.3. Overall Benefit: Risk Conclusion

Overall, the available data from non-clinical and clinical studies have not identified prohibitive risks associated with GSK3640254 at the exposures planned for this study. While there are a number of important potential risks identified for GSK3640254 and the study procedures, these can be addressed in this clinical trial with proper participant selection, close safety monitoring, and specific risk characterisation and mitigation.

3. OBJECTIVES AND ENDPOINTS

Objectives	Endpoints
Primary	

 To determine parent GSK3640254 and total drug-related radioactivity systemic concentrations following a single IV microtracer dose of [14C]-GSK3640254 (with an oral dose of non-radiolabelled GSK3640254) and oral dose of [14C]-GSK3640254¹ 	
 AUC(0–inf), AUC(0–t), Cmax, tmax and t1/2 of parent and total drug-related material (radioactivity) in plasma and blood. Volume of distribution at steady state (Vss) and clearance (CL) of parent after IV dose (Period 1 only). Renal clearance of parent (CLr) after both IV and oral dose Oral clearance (CL/F) and apparent volume of distribution (Vz/F) for the parent following oral administration

 To calculate the absolute oral bioavailability of GSK3640254 	
 Direct estimation of absolute oral bioavailability (F), indirect calculation of fraction of drug escaping first pass hepatic clearance (Fh), fraction absorbed (Fa) and fraction of drug escaping gut metabolism (Fg)

 To determine the rate and extent of excretion of total radioactivity in urine and feces and the total recovery of radioactivity, following IV and oral administration of [14C]-GSK3640254 	
 Urinary and fecal cumulative excretion as a percentage of the total radioactive dose
Secondary	

 To evaluate the safety and tolerability of GSK3640254 after single IV and oral doses in healthy participants. 	
 Characterize observed adverse events, and abnormal laboratory, 12-lead ECG, and vital signs assessments observed.

 To determine the blood:plasma ratio of [14C]-GSK3640254-related materials (total radioactivity) associated with blood cellular components 	
 Blood:plasma ratio of [14C]-GSK3640254-related materials (total radioactivity)

Exploratory	

 To generate samples that will be used to characterize the metabolite profile of GSK3640254 following a single IV microtracer dose of [¹⁴C]-GSK3640254 with an oral dose of non-radiolabelled GSK3640254 (plasma, urine, feces, duodenal bile) and a single, oral dose of [¹⁴C]-GSK3640254 (plasma, urine and feces, duodenal bile). 	
 Characterization and quantification of metabolites in plasma, urine, feces, and duodenal bile (qualitative identification in bile). These analytical investigations will be conducted, and the results reported under a separate GSK nonclinical protocol.

 To evaluate the PK and relative bioavailability of GSK3640254 following administration of the 85 mg suspension compared to the 200 mg tablet 	
 AUC(0-inf), AUC(0-t) and C_{max}

AUC(0–inf): Area under the plasma concentration-time curve from time zero (pre-dose) extrapolated to infinite time, AUC(0–t): Area under the plasma concentration-time curve from time zero (pre-dose) to last time of quantifiable concentration within a participant across all treatments, C_{max}: Maximum observed plasma concentration, t_{max}: time of occurrence of C_{max}, t_{1/2}: terminal phase half-life.

¹ For measured concentrations of GSK3640254 in plasma, the nomenclature [¹⁴C]-GSK3640254 describes the parent GSK3640254 concentration derived via analysis by liquid chromatography (LC) + AMS, whereas GSK3640254 describes the parent GSK3640254 concentration derived via liquid chromatography-tandem mass spectrometry (LC-MS/MS).

4. STUDY DESIGN

4.1. Overall Design

This is a single group, single center, [¹⁴C]-GSK3640254 mass balance study with a two-period, single sequence, and no masking.

This open-label, single-center, non-randomised, 2-period, single-sequence, mass balance study will enroll a cohort of 6 healthy male participants. The aim of the study is to assess the pharmacokinetics, balance/excretion, and metabolism of GSK3640254 using [¹⁴C]-radiolabelled drug substance administered as an IV infusion of a microtracer dose with an oral tablet, non-radiolabelled dose (Treatment period 1) and a [¹⁴C]-radiolabelled drug substance administered orally (Treatment Period 2).

Four to six healthy participants are deemed sufficient. To minimise the number of exposed to radiation, participants who discontinue early will not be replaced unless the total number of participants who complete dosing and all critical assessments drops below 4.

Each participant will be involved in the study for up to 10 weeks. He will have a screening visit, two treatment periods (Treatment Periods 1 and 2), separated by a washout period of at least 13 days between oral doses, and a follow-up visit 7 – 14 days after the last assessment in Treatment Period 2. During both treatment periods, participants will reside in the unit from the morning of Day -1 until all procedures are completed at 168 h post-dose (on Day 8). Participants may be asked to stay for up to 1 week longer in Treatment Period 2, if excretion of drug-related material takes longer than anticipated (see [Figure 1](#)).

Safety data will include AE reporting, 12-lead ECG, vital signs, and laboratory safety tests. Blood will be sampled extensively on the day of dosing and daily until Day 8, for assessing the PK of GSK3640254 and metabolites.

4.1.1. Screening Period

Participants must be screened within 30 days before the first dose of GSK3640254 and must meet all eligibility criteria.

Treatment Period 1 (oral tablets and ¹⁴C-intravenous infusion)

On Day 1 of Treatment Period 1, after an overnight fast of at least 8 h, each participant will take a single 200 mg oral dose (2 x 100 mg tablets) of GSK3640254 with a moderate fat meal (approximately 600 calories with approximately 30% of calories from fat); the IV infusion of 100 µg of [¹⁴C]-GSK3640254 (approximately 3.7 kBq; 100 nCi) will begin 5 h after oral dose and continue over 1 h. Blood samples, all voided urine, and feces will be collected continuously from Day 1 through Day 8, while duodenal bile will be collected as described below. Participants will be discharged on study Day 8 after completion of the 168-h sample collection and other planned assessments and instructed to return to the clinic on Day -1 of Treatment Period 2.

A non-invasive device (Entero-tracker) to collect duodenal bile will be used in Treatment Period 1. The bile string will be swallowed 2 h after the oral dose and 3 h before the IV infusion starts, a duration recommended to allow transit of the string to the duodenum. Participants will fast from insertion of the bile string until the completion of the IV infusion, at which point a food cue (small standard high-fat meal) will be given to stimulate gall bladder emptying. The Entero-tracker will be removed about 1.5 h after the IV infusion stops (7.5 h after the oral dose).

4.1.2. Treatment Period 2 (¹⁴C-oral suspension)

On Day 1 of Treatment Period 2, after an overnight fast of at least 8 h, each participant will receive approximately 85 mg [¹⁴C]-GSK3640254 (approximately 3.15 MBq; 85 µCi) as an oral suspension with a moderate fat meal (approximately 600 calories with approximately 30% of calories from fat). A non-invasive device (Entero-tracker) to collect duodenal bile will be used in Treatment Period 2. The Entero-tracker will be swallowed 2 h after oral dose. At 5.5 h after the start of oral dose, a food cue (small standard high-fat meal) will be given to stimulate gall bladder emptying. The collection bile string will be removed 1.5 h post the food cue (7 h after the oral dose) to capture the duodenal bile samples expelled from the gall bladder.

Blood, urine and fecal samples will be collected continuously from Day 1 through Day 8. Radioactivity quantification using liquid scintillation counting (LSC) will be performed on each 24-h urine collection and each 24-h fecal homogenate. Criteria for discharge for Period 2 are based on demonstrated cumulative recovery of radioactivity as outlined in Section 4.1.3. The inpatient stay may be extended by up to 7 days to meet the discharge criteria. In the unlikely event that excretion is still >1% in the 24-h collection period prior to discharge on Day 15, the participant will continue to collect fecal samples only, at home, at 24-h intervals. Samples will be returned to the unit every 2 to 3 days for analysis.

4.1.3. Demonstration of radioactivity recovery before discharge (Period 2)

LSC radio-quantification results from samples collected for Days 1 through 6 (through 144 h post-dose) will be reviewed on Day 8. The GlaxoSmithKline (GSK) In vitro / In vivo Translation (IV/IVT) Study Monitor should be consulted to agree with release of a participant. This process is outlined in detail in the Study Reference Manual (SRM).

- If >90% of the administered radioactivity has been recovered from the Day 1-6 samples, then the participant may be discharged on Day 8 after all scheduled assessments have been completed, including complete collection of Day 7 urine and feces samples (24 h collection period ending on Day 8).
- If ≤90% has been recovered, then the radio-quantification results will be re-evaluated on Day 9 with Day 7 results included.

On Day 9, if >90% has been recovered or <1% of the dose has been excreted on both Day 6 (120-144 h) and Day 7 (144-168 h), then the participant may be discharged on Day 9.

If the participant is not eligible for discharge on Day 9, or if the results are inconclusive, the participant will remain at the unit. Urine and fecal collections will continue at 24-h intervals for up to 7 additional days (until the morning of Day 15). Once <1% of the dose is recovered in 2 consecutive 24-h periods where samples are provided (and the samples were of sufficient size to make this assessment), or once >90% of the radioactivity has been recovered, the participant will be discharged.

All remaining participants will be discharged from the unit no later than Day 15. In the unlikely event that excretion is still $\geq 1\%$ in the 24-h collection period prior to discharge on Day 15, the participant will continue to collect fecal samples only, at home, over 24-h intervals. Samples will be returned to the unit every 2 to 3 days for analysis.

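### Required home fecal collection after Day 15 hangs on one 24-h result that is probably not available until after discharge, and its trigger is looser than the in-unit release rule, so late excretion can go uncollected

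*Protocol*

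**What the plan says.** Protocol 4.1.3 sets the Period 2 discharge timetable.

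- **First review:** "LSC radio-quantification results from samples collected for Days 1 through 6 (through 144 h post-dose) will be reviewed on Day 8".
- **Second review:** at 90% or less recovered, "then the radio-quantification results will be re-evaluated on Day 9 with Day 7 results included".
- **Extension:** "Urine and fecal collections will continue at 24-h intervals for up to 7 additional days (until the morning of Day 15").
- **In-unit release:** more than 90% recovered, or excretion below 1% "recovered in 2 consecutive 24-h periods where samples are provided (and the samples were of sufficient size to make this assessment").
- **Latest discharge:** "All remaining participants will be discharged from the unit no later than Day 15".
- **Home collection:** required if excretion of 1% or more persists "in the 24-h collection period prior to discharge on Day 15, the participant will continue to collect fecal samples only, at home, over 24-h intervals".

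The home-collection rule also appears in the synopsis (1.1), the schema footnote (1.2), 4.1.2 and SAP 1.3. All four put the threshold at above 1%, whereas 4.1.3 has at or above 1%. The schema footnote ties the trigger to the collections immediately before discharge. A separate synopsis sentence allows home collection of excreta, not feces alone, where it is judged necessary to show sufficient recovery. Section 4.1.4 lets follow-up be extended if excretion is above 1%.

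**The concern.** Two features of the Day 15 step do not fit the rest of 4.1.3.

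The first is timing. The deciding collection ends on the morning of the latest discharge day. If it is read with the same delay as earlier collections, the site does not know on Day 15 for whom home collection is required, and the text does not say what happens while the result is pending.

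The second is the criterion. The in-unit rule asks for two consecutive low periods, counts only periods with adequate samples, and otherwise requires more than 90% recovered. The Day 15 trigger looks at one period, with no adequacy condition and no reference to cumulative recovery.

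Total recovery of radioactivity belongs to a primary objective, and 4 to 6 participants are planned. Those still resident on Day 15 are the ones whose recovery has not been shown to be complete. In SAP 5.2.1.2.2, cumulative recovery is a plain sum of what was collected. Late excretion that is not collected therefore looks the same as retention in the body.

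**Working it through.** **Timetable (inputs from 4.1.3).** The Day d collection covers 24(d-1) to 24d h and ends on the morning of Day d+1.

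| Collection | Interval | Ends | Result reviewed | Lag |
|---|---|---|---|---|
| Day 6 | 120-144 h | Day 7 | Day 8 (stated) | 1 day |
| Day 7 | 144-168 h | Day 8 | Day 9 (stated) | 1 day |
| Day 14 | 312-336 h | Day 15 | Day 16 (inferred) | 1 day |

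The protocol's end point reproduces: 168 + 7 x 24 = 336 h, the morning of Day 15. At a one-day lag, the newest result on Day 15 is that of Day 13.

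**The two rules side by side.** Take a man with 3% on Day 13, 0.8% on Day 14 and 80% cumulative. He does not exceed 90% and does not have two consecutive periods below 1%, so he fails the in-unit rule. His last period is below 1%, so home collection is not required.

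**Size, smooth decline.** Assume a first-order tail with daily ratio r = 2^(-24/t½) and 0.8% of dose on Day 14. The half-lives are assumptions; neither document gives one for late excretion.

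| t½ | r | Day 13 = 0.8/r | Next day = 0.8r | All remaining = 0.8r/(1-r) |
|---|---|---|---|---|
| 24 h | 0.500 | 1.60% | 0.40% | 0.80% |
| 36 h | 0.630 | 1.27% | 0.50% | 1.36% |
| 48 h | 0.707 | 1.13% | 0.57% | 1.93% |

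For one such participant, the effect on the mean runs from 0.80/6 = 0.13 to 1.93/4 = 0.48 percentage points. This describes the tail only. Carried back over Days 1-14, 0.8% on Day 14 at 24 h would imply 0.8 x (2^14 - 1) = 13,106% of dose.

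**Size, first-order from dosing.** Assume t½ = 72 h (r = 0.794), stool every day and 90% of dose ultimately recoverable. Day 13 is 90(r^12 - r^13) = 1.16%, Day 14 is 90(r^13 - r^14) = 0.92%, and the total to Day 14 is 90(1 - r^14) = 86.5%. He fails the in-unit rule and does not trigger home collection. The remainder is 90r^14 = 3.5% of dose, or 0.6 to 0.9 points on the mean of 6 or 4.

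**Size, no stool on Day 14.** The rat data in Appendix 6 give 99.96% fecal excretion, and inclusion criterion 3 requires bowel movements only averaging one or more a day. If man is similar, a day without stool reads near 0%. Assume t½ = 96 h (r = 0.841) and full recoverability. Recovery through Day 13 is 100(1 - r^13) = 89.5%, and Day 13 is 2.0%. With stool, Day 14 would read 1.7% and trigger; without stool it does not, and 100r^13 = 10.5% of dose remains. One home stool on Day 15 would add 100(r^13 - r^15) = 3.1% and take him to 92.6%, past the 90% criterion.

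**Simulation.** With stool on 70-85% of days and t½ of 96-168 h, about 15-30% of those still resident on Day 15 were not triggered, with a mean of about 10-29% of dose uncollected. With daily stool at those half-lives, none were missed.

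**The case against.** The protocol leaves room for judgment. The synopsis permits home collection whenever it is judged necessary, 4.1.3 asks that the sponsor's study monitor be consulted on release, 4.1.4 permits extended follow-up, and 1.3 lets the timing and number of assessments change without an amendment. A reader might infer that one last period below 1% ends all collection. The documents do not support that: the fixed trigger says when home collection is mandatory, not when it is forbidden.

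The one-day lag is also inferred. No turnaround is stated for Days 10-15, and 4.1.3 refers to the Study Reference Manual, which is not among the documents. The wording that the participant will continue to collect can be read as unbroken collection, and nothing stops a site from sending containers home on Day 15.

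The size may be small. Under smooth decline the in-unit rule itself accepts a tail once two periods fall below 1%. In the 0.8% illustration, Day 15 would also be below 1%, so the extra collection that the in-unit rule requires is about one interval, 0.4-0.6% of dose. The large simulated losses need slow excretion and days without stool, although participants must have regular bowel movements and 5.3.1 encourages hydration and allows prunes. The protocol itself calls the Day 15 case unlikely.

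All of this limits the size and certainty of the loss. It does not remove the gap. The discretionary provisions are optional, the synopsis gives no numerical criterion, and the examples in 4.1.4 do not include excreta collection. The trigger still lacks the adequacy condition that the in-unit rule has.

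**Conclusion.** The point holds as a mismatch between the mandatory home-collection trigger and the in-unit release rule, together with a deciding result that, at the implied lag, arrives about Day 16. Loss of late excretion is possible, not certain.

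Under smooth decline with 0.8% on Day 14, at most about 0.8, 1.4 or 1.9% of dose goes uncollected at half-lives of 24, 36 or 48 h, which is about 0.1-0.5 points on the mean. Slower excretion or a day without stool makes it larger: 3.5% and 10.5% of dose in the two worked cases. These are total remainders, so they are upper limits on what home collection would recover. All rest on assumed half-lives; the last also assumes predominantly fecal excretion in man.

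A reader might infer that a man still excreting 2% on Day 14 would never be asked to collect. That does not follow, because 2% meets the trigger. His exposure is the interval lost if the site waits for the result: 0.50, 0.63 or 0.71 of the Day 14 amount at 24, 36 or 48 h.

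**What to change.** In protocol 4.1.3, and to match in 1.1, 1.2 and 4.1.2, replace the single-period trigger with a default. Any participant still resident on Day 15 who has not been shown, on the results to hand, to meet the in-unit criterion (more than 90% recovered, or below 1% in two consecutive periods with adequate samples) starts home fecal collection at 336 h. Collection stops when the pending and returned results from adequate samples meet that same criterion. This uses the protocol's own rule, removes the dependence on a pending result, and supplies the stopping rule for home collection that the text lacks.

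In the same edit, reconcile the threshold (above 1% in 1.1, 1.2, 4.1.2 and SAP 1.3; at or above 1% in 4.1.3) and the matrix (excreta in one synopsis sentence; feces only in 4.1.3).

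The cost is protocol wording plus a few collection kits and scintillation counts for those still resident on Day 15. The downside is that some participants will collect one or two days of feces that prove unnecessary.

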4.1.4. Follow-up

Follow-up procedures will be done 7-14 days after the participant's last assessment in Treatment Period 2. The follow-up period may be extended if:

- (i) radioactivity excretion is still higher than 1%;
- (ii) a participant has an unresolved AE at the follow-up visit, which, in the opinion of the investigator, merits further follow-up; or
- (iii) new information becomes available that supports an extended follow-up period.

The investigator and GSK IV/IVT Monitor and/or GSK Medical Monitor as appropriate will agree on the nature of the extended follow-up. For example, participants may have a telephone follow-up at which they are asked about AEs, or participants may be asked to attend extra outpatient visits for additional monitoring of plasma radioactivity levels and/or for extra safety tests. The extra safety tests might include tests that are not described in this protocol. The investigator reserves the right, during or after the study, to repeat safety tests or to do any extra safety tests that are in the best interest of the participants. Those extra tests may or may not be described in this protocol.

4.2. Scientific Rationale for Study Design

In the first treatment period of this study, an IV microtracer dose of [^{14}C]-GSK3640254 will be infused over 1 h, beginning 5 h after an oral dose of non-radiolabelled GSK3640254 (tablets). The non-radiolabelled 200 mg dose of GSK3640254 is to ensure that the PK of the microdose represents a therapeutically relevant total body exposure to the drug. In the second treatment period, an 85 mg oral suspension of [^{14}C]-GSK3640254 will be used for comparison.

Biliary elimination pathways will be characterised after the IV and oral doses by inclusion of duodenal bile collection in both Treatment Periods 1 and 2. Complexities in human fecal sample analysis such as extraction, stability in the gastrointestinal tract, and endogenous contamination are minimised through assessment of the metabolite profile in duodenal bile after IV drug administration.

In order to characterize potential biliary elimination pathways, this study will also employ the Entero-Tracker for sampling of duodenal bile to conduct qualitative assessment of drug metabolites in this matrix. The Entero-Tracker is based on a similar device, Entero-Test which has been shown to be an easy-to-use and minimally-invasive method for sampling bile from the duodenum (Guiney, 2011). The Entero-Tracker is a recent replacement device for Entero-Test that is an Food and Drug Administration (FDA) 510k exempt device. Information on the biliary disposition of drug-related material derived in the current study may avoid the need for invasive methods of bile collection in future studies

Details of blood, bile, urine and fecal sample collection and processing, storage and shipping procedures are detailed in the SRM.

4.3. Justification for Dose

Based on modelling and simulation of virology and PK data, coupled with an ongoing proof of concept (POC) study for GSK3640254 (208132) in HIV-infected participants, the currently projected therapeutic dose range to be investigated in Phase IIb is 50-200 mg once daily. The population PK model of GSK3640254, including parameter uncertainty, was integrated with the PK/Pharmacodynamic (PD) model of GSK3532795 and the distribution of protein binding adjusted (PBA) EC90 values obtained with GSK3640254 from an in vitro experiment with 36 Gag/PR genotyped viruses (e.g. mean of 19.1 ng/mL with CV% of 33%). Further details of the findings in this study are provided in the IB.

The 100 µg microtracer dose administered as a 1 h IV infusion in Treatment period 1 is projected (based on allometry and a conservative assumption of 15% oral bioavailability) to achieve a GSK3640254 C_{max} ~3 ng/mL, which is >200-fold lower than the geometric mean C_{max} following a single 200 mg dose in healthy participants (Study 207187) and >400 fold lower than the geometric mean C_{max} following a single 200 mg dose in HIV-infected patients. This dose can be categorised as a microdose and as such the required safety cover is detailed in International Council for Harmonisation of Technical Requirements for Pharmaceuticals for Human Use (ICH) M3 (R2) ([International Conference on Harmonisation](#), 2009.) In Treatment Period 2, the ¹⁴C labelled solution dose of GSK3640254 is 85 mg (85 uCi) which is partly based on practical limitations and is well within the target dose range to be evaluated in Phase IIb studies.

Preclinical toxicology species provide safety cover for systemic exposure to GSK3640254. Predicted steady-state exposures for a projected 200 mg QD maximum dose in Phase IIb are essentially equal to the no-observed adverse-effect-level (NOAEL) exposure in a 4-week oral toxicity study in rats, although no NOAEL was identified in dogs for GI intolerability and minimal effects of parietal cells following 4 weeks of dosing. However, in this single dose design absorption, distribution, metabolism, and excretion (ADME) study of very limited drug exposure these findings become less relevant.

In vitro studies using hepatocytes from nonclinical species and humans show that there is generally no qualitative difference in metabolites formed. Preliminary non-radiolabelled

studies showed that GSK3640254 was the predominant drug-related component with low levels of oxidative metabolites in human plasma following repeat oral doses of 320 mg/day (see IB, Section 1.1).

